- Currently, or in the last three years, have implemented systemic practice in their keyworker teams. This includes systematic training in systemic practice for keyworker or the hiring/commissioning of Psychotherapists or Clinicians to support keyworkers.
- Were initial Families First for Children DfE pathfinder local authority; or
- Currently, or in the last two years, have an inadequate Children's Services Ofsted rating.

Recruitment

Local authorities were recruited via an Expression of Interest (EOI) hosted on Coram's website. The EOI was advertised through a number of routes including a press release from Coram, IFT and Ecorys, several sector press articles as well as a number of notices including by ADCS and in the DfE DCS newsletter. In addition, the then Supporting Families Programme hosted a webinar and posted repeatedly on their weekly newsletter. The Programme also advertised it through their local authority development team and via DfE's social care regional programme advisors.

Coram assessed the EOIs and then undertook randomisation of 12 local authorities. Since randomisation occurred, two local authorities in the control arm have dropped out of the trial, resulting in a total sample of ten local authorities, six in the intervention arm and four in the control arm.

Reasons for dropout included limited capacity for additional data collection and decisions to implement systemic practice and training in the local authority in the pilot period. One of the local authorities was embarking on a new framework and practice standards which included systemic principles alongside a wider change programme within the local authority which limited their capacity to implement new approaches to outcome collection with families. The other local authority also wished to implement systemic practice within the pilot period. They also noted that the required additional data collection would be too burdensome on staff and family time and require additional resources to oversee and quality assure the processes, particularly as they would have fell outside their current established measurement system already in place.

Within the pilot local authorities, all keyworkers in both control and intervention local authorities will take part in the study.

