All costs will be adjusted to constant prices using GDP deflators. The base year used should be the year in which delivery begins. Cost estimates will be generated assuming full compliance (i.e. keyworkers attend all sessions). Costs will be separated into prerequisite, set-up and recurring. Recurring costs will be calculated for one financial year (i.e. one round of delivery) of ongoing delivery. For example, the cost of the local authorities' systemic practice lead, ongoing training, maintenance of the virtual practice hub. Total costs will be presented for one financial year for an average cohort of keyworkers as well as for families receiving keyworker support. We will also attempt to calculate costs per participant figures (keyworker and families) should be presented for set-up, recurring and total costs.

Costs will be presented as a full list and description of the items included in the cost; and, a detailed breakdown of cost estimates by item and each organisation.

Feasibility for a full-scale trial

Trial feasibility will be answered using findings from both IPE and pilot RCT via the following questions:

1. Is there a clear description of the systemic practice model that would allow it to be implemented and evaluated in other local authorities? Are any changes needed to before further rollout?
2. Does the systemic practice model show enough promise of impact to take to a full trial?
3. What is the recommended approach for further evaluation?
4. What are the implications for family help and early help as well as wider policy and practice?

From this the evaluation will provide critical learning about recruitment, capacity of local authorities to implement systemic practice, fidelity, dosage, feasibility of data collection and appropriateness of measures, sample size for statistical power, expected effect size, follow-up sequencing, and identify any unintended consequences.

To assess the feasibility for a full scale trial the following progression criteria using pre-determined thresholds has been developed in line with standard evaluation practice⁹⁸ and with the pilot's expert working group. A set of criteria, RAG rated for 'stop,' 'amend' and 'go' is set out in the table below.

As a guide:

- If at least 10 out of the 12 'proceed' criteria are met, we will recommend proceeding to a full trial
- If there are at least 10 'review' criteria met, we will recommend reviewing before moving to a full trial

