- If there are more than 6 'stop' criteria met, we will recommend not proceeding to a full trial

⁹⁸ Avery K., et al (2017) Informing efficient randomised controlled trials: exploration of challenges in developing progression criteria for internal pilot studies. *BMJ Open*. doi: 10.1136/bmjopen-2016-013537.

Table 13: Criteria for full-scale trial

| Criteria | Green (proceed) | Amber (review) | Red (stop) |
|---|--|--|---|
| 1. Adequate recruitment of local authorities into the trial | ≥10 local authorities recruited | ≥8 local authorities recruited | <5 local authorities recruited |
| 2. Adequate retention of local authorities within the trial (an indicator of acceptability of randomisation) | No local authorities drop out of the trial | 1-3 local authorities drop out of the trial | ≥4 local authorities drop out of the trial |
| 3. Adequate recruitment rate of families into the trial and completion of baseline Family Outcome Questionnaire | 80-100% (n=932-1165) families complete baseline measures | 60-79% (n=699-931) families complete baseline measures | 0-59% (n=0-698) families complete baseline measures |
| 4. Adequate response/attrition rate to the trial | 50-100% families complete endline measures | 35-49% families complete endline measures | 0-34% families complete endline measures |
| 5. Adequate follow-up data from the keyworker survey | ≥200 keyworker follow-up measures completed | ≥175 keyworker follow-up measures completed | <150 keyworker follow-up measures completed |
| 6. Minimal Family Outcome Questionnaire data loss/unusable due to poor quality data | 10% of outcome data lost to poor quality data | 15% of outcome data lost to poor quality data | 20% of outcome data lost to poor quality data |

| Criteria | Green (proceed) | Amber (review) | Red (stop) |
|--|--|--|---|
| 7. Sufficient administrative data on families collected from local authorities to allow for analysis | Low rates of missing administrative data (>75% of family cases complete) | Some missing data (>60% of cases complete) | High rates of missing data (<50% of cases complete) |
| 8. Evidence of promise according to the primary outcome of progression towards goals | The MDES of the study is ≤ 0.50 | The MDES of the study is between 0.51-1 | The MDES of the study is > 1 |

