| 9. Sufficient fidelity to trial protocol | Low rates of deviation from the trial protocol, as measured by incidents of trial arm contamination (80-100% of cases) | Moderate rates of deviation from the trial protocol, as measured by incidents of trial arm contamination (70-79% of cases) | High rates of deviation from the trial protocol, as measured by incidents of trial arm contamination (0-69% of cases) |
| 10. Sufficient fidelity to systemic practice intervention | Low rates of deviation from the intervention theory of change according to the fidelity checklist | Moderate rates of deviation from the intervention theory of change according to the fidelity checklist | Low rates of deviation from the intervention theory of change according to the fidelity checklist |

Further considerations beyond these progression criteria would also support assessing the feasibility of a full trial. We suggest these should include:

- An assessment of how many local authorities in England would be provisionally eligible for a full trial to enable adequate recruitment, in that they i) currently, or in the last three years, have not implemented systemic practice in their keyworker teams; and ii) currently, or in the last two years, have not had an inadequate Children's Services Ofsted rating

A consideration of barriers, enablers, and unintended consequences as identified in the implementation and process evaluation. Key mechanisms for change identified in this

evaluation should be reviewed and considered as part of the practice model before progressing to a full trial.

Ethics

We will use Coram's well-established research ethics standards to ensure ethical rigour. These standards are based on guidelines from the Economic and Social Research Council, the Social Research Association, and the UK Research Integrity Office.

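### The progression rule counts 12 criteria but Table 13 lists 10, and with one row already amber the proceed threshold cannot be met on the table as printed

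*Protocol*

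**What the plan says.** Establishing whether a full trial is feasible is one of the pilot's two primary aims. The protocol section *Feasibility for a full-scale trial* introduces pre-set thresholds developed with the expert working group and turns them into a recommendation with three bullets, offered as guidance:

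- *Proceed*: "If at least 10 out of the 12" criteria are green, a full trial is recommended.
- *Review*: at least 10 amber "criteria met, we will recommend reviewing before moving to a full trial".
- *Stop*: more than 6 red.

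Table 13 then lists the criteria, numbered 1 to 10 without a gap. The text after row 10 moves on to considerations that it describes as lying outside the progression criteria; these carry no colour thresholds.

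Row 1 (authorities recruited) is green at 10 or more, amber at 8 or more and red below 5. Row 2 (authorities retained) is green only if none leaves, and amber if "1-3 local authorities drop out of the trial". The *Recruitment* section reports that, after 12 authorities were randomised, "two local authorities in the control arm have dropped out of the trial".

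**The concern.** The rule and the table it counts do not match. Ten greens out of twelve leaves room for two weaker rows; ten greens out of ten leaves none, and one row is already known not to be green. The rule also has no outcome for mixed ratings, so the best result still attainable, 9 green and 1 amber, meets none of the three bullets.

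Several rows cannot be scored as printed either. If the rule cannot return an answer, the recommendation on one of the primary aims will be settled by judgement once results are known, which pre-set thresholds are meant to prevent.

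**Working it through.** **Inputs.** Proceed ≥10 green, review ≥10 amber, stop ≥7 red (*Feasibility for a full-scale trial*). Table 13 rows: 10. Authorities randomised 12, lost 2, remaining 10 (*Recruitment*).

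**The stated total.** Counting the rows of Table 13 gives 10, so the protocol's figure of 12 is not reproduced.

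**Rows already determined.** Row 1: both 12 and 10 are ≥10, so green. Row 2: 2 lost lies in 1–3, so amber.

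**Largest attainable counts with rows 1 and 2 fixed:**

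| Rows in table | Max green | Max amber | Max red |
|---|---|---|---|
| 10 (as printed) | 1 + 8 = 9 | 1 + 8 = 9 | 8 |
| 12 (if two were omitted) | 1 + 10 = 11 | 1 + 10 = 11 | 10 |

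On the printed table proceed fails (9 < 10), review fails (9 < 10) and stop is possible (8 ≥ 7). With 12 rows all three are possible.

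**Patterns of the other eight rows.** Three colours on eight rows give 3^8 = 6,561 patterns.

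- Proceed: 0. Review: 0.
- Stop (7 or 8 red): 8 × 2 + 1 = 17.
- No recommendation: 6,561 − 17 = 6,544.

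These are counts of patterns, not probabilities.

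**Alternative reading of row 1.** Its amber cell is open upwards (≥8), so 10 authorities also satisfy it literally. If row 1 is counted there too, amber can reach 10, but only when every other row also meets its amber cell. Proceed is unaffected: row 2 stays amber and the maximum green stays 9.

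**The plan's share carried to 10 rows.** 10/12 = 83.3%; 0.833 × 10 = 8.33, so 9 rows are needed. Eight rows would be 8/10 = 80%. For stop, 6/12 = 50%, so more than 5 of 10.

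**Individual rows:**

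- Row 10: Green and Red carry the same text, "Low rates of deviation from the intervention theory of change according to the fidelity checklist".
- Row 9: Green speaks of low deviation, "as measured by incidents of trial arm contamination (80-100% of cases"; taken literally, contamination in 80–100% of cases is green and in 0–69% is red.
- Row 5: ≥200, ≥175 and <150 leave 150–174 keyworkers unclassified.
- Row 7: >75%, >60% and <50% leave 50–60% unclassified.
- Row 6: only the points 10%, 15% and 20% are defined.
- Row 1: 5–7 authorities are unclassified, but this is moot with 10 remaining.
- Row 4: Green is "50-100% families complete endline measures", with no denominator named.

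**The case against.** The strongest reply is that the bullets are offered only as guidance. The same section answers feasibility through four questions drawing on both the process evaluation and the pilot trial, and it adds considerations beyond the table. That stands. A reader might infer that even an excellent pilot could not lead to a full trial; the protocol does not support this, because the evaluators may depart from the count. It remains true that the count cannot return proceed on the printed table.

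A second reply is that the figure of 12 may be right and the table incomplete. The unbroken numbering and the text that follows row 10 make lost rows unlikely, but the protocol does not show which figure is wrong. The finding is therefore conditional on the table as printed.

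A reader might also infer that stop is the only verdict left. That holds if row 1 is scored green only; on the open reading of its amber cell, review is reachable in a narrow case.

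Another tempting inference is that row 4 is heading for amber because *Sample size calculations* expects 560 analysable families of 1,165 at baseline (560/1,165 = 48.1%, below 50%). The documents do not support it. *Data collection* accepts a baseline plus either a midline or an endline questionnaire and requires at least 10 weeks of work with the family, so the 560 are not a count of endline completers. Row 4 names no denominator, and a target may properly exceed a cautious planning figure.

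Finally, the wording of rows 9 and 10 is plainly a slip. The title of row 9 shows that 80–100% is meant as adherence. These cells need correcting but do not add to the seriousness of the main point.

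**Conclusion.** The concern holds for the rule as written. Table 13 has 10 criteria where the rule counts 12; row 2 is amber; at most 9 rows can be green against the 10 required. Proceed is unreachable unless two criteria are missing from the table. Review is unreachable if row 1 is scored green only, and reachable on the open reading only if every other row meets amber. Most patterns give no recommendation.

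This rests on two assumptions: that the printed table is complete, and that the two exits count under row 2. The second is well supported, since *Recruitment* describes them as leaving the trial after randomisation and row 2 sets no start date. No outcome estimate is affected. What is affected is the pre-set test for one of the two primary aims, so it should be corrected before the analysis that Annex A schedules for August 2026.

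**What to change.** Agree the following with the expert working group and record it before outcome data are analysed:

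1. **Reconcile the count with the table.** Either restore the two missing criteria with their colour thresholds, or restate the rule on 10 rows.
2. **If 10 rows are kept, state the bar openly.** Keeping the 10/12 share means 9 of 10 green, which now requires every row except row 2 to be green. Choosing 8 of 10 lowers the bar to 80% and should be recorded as a lowering.
3. **Make the rule exhaustive.** Stop if more than half the rows are red; review for every pattern that is neither proceed nor stop.
4. **Correct the cells.** Row 10 Red should refer to high rates of deviation. Row 9 should be the percentage of cases without contamination. Rows 5, 6 and 7 need contiguous bands, with the cut-offs chosen by the working group.
5. **Row 4:** state the denominator only. The ratio 560/1,165 is not a reason to lower the 50% threshold.

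The cost is an edit to one table and three bullets, plus the working group's agreement. No data collection changes.

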Eligibility for the pilot study also has the advantage of being determined by eligibility for support by keyworkers meaning that all families supported by a keyworker will be eligible to be included within the trial, if they consent to take part when completing the Family Outcomes Questionnaire. For families that do not consent to take part in the trial, we will request aggregate level anonymous data about these families from local authority case management administrative data. This will allow us to compare the characteristics of those who do and do not consent to the trial. This will include potential biases across characteristics such as type of need at referral, whether they are being re-referred as well as demographic characteristics such as, sex, race and ethnicity, and disability.

Coram was responsible for randomisation and undertook internal quality assurance checks to minimise any biases.

Coram will also explore the influence of trial arm allocation compliance using Complier Average Causal Effect Analysis (meaning whether families or keyworkers in the intervention arm receive the intervention), by including intervention receipt in an instrumental variable analysis. Keyworkers in the intervention arm that attend at least 80% percent (four out of five days) of the initial five-day systemic practice training for all keyworkers will be deemed compliant. This threshold of 80% was recommended by IFT based on their extensive experience of keyworkers being able to use and embed systemic training in their practice. IFT and the local authorities will record attendance of keyworker training which will be included in the administrative data collected.

Quality assurance of the Family Outcome Questionnaire data will be undertaken frequently, and any missing, anomalous or any potential biases in the data will be queried with the respective local authority. If any consistent issues are identified, additional guidance and targeted training for keyworkers and additional guidance within the questionnaire for families will be provided to help ensure compliance.

Implementation fidelity will be measured according to the core components of the systemic practice pilot. This is set out in the table below.

Table 10: Implementation fidelity measures for intervention local authorities

| Component of fidelity | Measure | Source |
|--------------------------------------|---|---|

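### Table 13 cannot be applied as printed: row 10 has the same text for proceed and stop, row 9's percentages contradict its words, and other rows leave values unrated

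*Protocol*

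**What the plan says.** The section on feasibility for a full-scale trial sets out progression criteria with thresholds fixed in advance and rated green, amber or red. As a guide, it recommends proceeding if at least 10 of 12 criteria are green, reviewing if at least 10 are amber, and not proceeding if more than 6 are red. Table 13 prints ten criteria.

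- **Row 10, fidelity to the intervention.** Green: "Low rates of deviation from the intervention theory of change according to the fidelity checklist". Amber: "Moderate rates of deviation from the intervention theory of change according to the fidelity checklist". Red repeats the green cell word for word.
- **Row 9, fidelity to the trial protocol.** Green: "Low rates of deviation from the trial protocol, as measured by incidents of trial arm contamination (80-100% of cases". Amber: "Moderate rates of deviation from the trial protocol, as measured by incidents of trial arm contamination (70-79% of cases". Red: "High rates of deviation from the trial protocol, as measured by incidents of trial arm contamination (0-69% of cases".
- **Row 5, keyworker follow-up.** Green starts at 200. Amber and red read "≥175 keyworker follow-up measures completed | <150 keyworker follow-up measures completed".
- **Row 7, administrative data.** Green is above 75% complete. Amber and red read "Some missing data (>60% of cases complete) | High rates of missing data (<50% of cases complete".
- **Row 6, poor-quality outcome data.** The three cells give single values of 10%, 15% and 20%.
- **Row 1, recruitment of local authorities.** Green is 10 or more, amber 8 or more, red fewer than 5.
- **Row 2, retention of local authorities.** Green is no dropout, amber 1 to 3, red 4 or more.

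**The concern.** Establishing whether a full trial is feasible is one of the pilot's two primary aims, and Table 13 is its formal decision tool. A threshold set in advance is useful only if one result leads to one rating. Row 10 fails that test outright, because one result earns two opposite ratings and the worst result earns none. Row 9 fails it unless the reader overrides either the words or the numbers. The gaps in the other rows leave room to choose a rating after the results are known. The thresholds stand in the protocol itself, so this is not detail left for a statistical analysis plan.

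**Working it through.** No sample size or power figure is involved. The check compares the cells, passes values through the bands, and counts ratings against the guide.

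**Row 10.** The green and red cells are identical and the amber cell differs. Low deviation meets green and red, moderate deviation meets amber, and high deviation meets no cell.

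**Row 9.** The printed bands are 80-100 green, 70-79 amber and 0-69 red. The percentage can be read in two ways:

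| Cases contaminated | Percentage read as contaminated cases | Percentage read as cases free of contamination |
|---|---|---|
| 0% | red | green |
| 5% | red | green |
| 20% | red | green |
| 25% | red | amber |
| 31% | red | red |
| 50% | red | red |
| 70% | amber | red |
| 80% | green | red |
| 100% | green | red |

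Under the first reading the numbers run against the words low, moderate and high. Under the second they agree: 0-20% contaminated is green, 21-30% amber and 31-100% red. Neither the table nor its introduction says which is meant, and the only measure named is incidents of contamination.

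**Unrated values.**

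| Row | Green | Amber | Red | Left unrated |
|---|---|---|---|---|
| 1 | ≥10 | ≥8 | <5 | 5-7 (moot: 12 authorities randomised, 10 remain) |
| 5 | ≥200 | ≥175 | <150 | 150-174 |
| 6 | 10% | 15% | 20% | values between the points, such as 12% or 17% |
| 7 | >75% | >60% | <50% | 50-60% |

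**Effect on the overall recommendation.**

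- *Stop* needs more than 6 reds, that is, at least 7. Rows 9 and 10 supply at most 2, so at least 7 − 2 = 5 other rows must already be red.
- *Proceed* needs 10 greens. Two control authorities dropped out after randomisation, so row 2 is amber. On the ten printed rows at most 10 − 1 = 9 greens remain, whatever rows 9 and 10 say.
- If twelve criteria exist, at most 12 − 1 = 11 greens remain. Losing both rows 9 and 10 leaves 11 − 2 = 9, below the 10 required. Only in that case can these two rows decide *proceed*.

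**The case against.** The strongest reply is that any reader can see what was meant. Row 10's red cell is a copying slip for high, as its own amber cell and the low, moderate, high pattern of row 9 show. Row 9 is titled as sufficient fidelity to the protocol, so 80-100% reads naturally as the share of cases that adhere. Row 6's three values can be taken as cut-points, with 0% loss plainly green. The counts are offered only as a guide, and the text after the table adds further considerations.

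Much of this stands. The intended meaning of rows 9 and 10 is probably clear, and the table is not a mechanical rule. But the likely intention is not what is printed, and a loss of 12% or 17% in row 6 still cannot be placed.

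A reader might also infer that good conduct could trigger the overall stop, or that a heavily contaminated trial would be recommended for scaling up. The documents do not support either. These two rows cannot reach more than 6 reds by themselves, and rating heavy contamination green requires ignoring the word low in the same cell.

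Nor do the dropouts show that contamination is present in the remaining sample. The Recruitment section does link both departures to adopting systemic practice or principles, but it also cites data-collection burden and limited capacity, and those authorities have left. The Compliance and fidelity section gives reasons why randomising whole authorities keeps the risk low.

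**Conclusion.** The point holds as a defect in the printed thresholds. Row 10 contradicts itself and leaves high deviation unrated. Row 9's words are in the right order, but its percentages contradict them unless they mean cases free of contamination, which is not stated. Rows 5 and 7 have gaps of 150-174 follow-ups and 50-60% completeness, and row 6 has points where bands are needed. Row 1's gap has no effect here. It would go too far to call half the table unusable, since rows 5 and 7 work outside their gaps.

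The consequence for the final recommendation is bounded. Rows 9 and 10 cannot produce the overall stop alone. On the printed table they cannot change *proceed*, which is already unreachable. They could decide it only if two further criteria exist, so the mismatch between twelve criteria and ten rows is part of the same problem. This rests on counting the two control authorities as dropouts under row 2.

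**What to change.** Make these changes before analysis, which Annex A places in August 2026:

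1. **Row 10, red:** change to high rates of deviation. No new fidelity metric is needed for this. The Compliance and fidelity section already states that "Implementation fidelity will be measured according to the core components of the systemic practice pilot".
2. **Row 9:** label the percentages as the share of cases free of contamination, keeping 80-100% green, 70-79% amber and 0-69% red.
3. **Rows 5, 6 and 7:** make the bands contiguous. The expert working group should choose whether amber or red absorbs each gap, since the protocol favours neither. For row 6, one example is ≤10% green, >10% to <20% amber and ≥20% red.
4. **Overall guide:** reconcile the twelve criteria with the ten rows, either by printing the missing two or by restating the counts.

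The cost is a wording change to one table and its introduction, with no new data. The downside is that some results now unrated would receive an amber or red rating.
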